1. PROTOCOL SYNOPSIS

Clinical Protocol: ESR-20-21010, UCCC-GI-21-01

Study Title: Durvalumab (MEDI4736) and Tremelimumab for Hepatocellular Carcinoma in Patients Listed for a Liver Transplant
Protocol Number: ESR-20-21010
Clinical Phase: II
Study Duration: Four years to complete accrual. Survival follow up will continue for 5 years.
Investigational Product(s) and Reference Therapy: 
 1. Durvalumab concentrate for solution for infusion will be supplied in glass vials containing 500 mg durvalumab at a concentration of 50 mg/mL. 2. Tremelimumab concentrate for solution for infusion will be supplied in glass vials containing 25 mg tremelimumab at a concentration of 20 mg/mL. 3. Locoregional therapy will be per institutional standards of care.
Research Hypothesis: Immunotherapy can safely downstage patients and achieve durable systemic disease control to improve clinical outcomes in HCC patients undergoing liver transplant.
Objectives: Primary Objectives: 
 1. To assess the safety of immunotherapy for treatment of HCC in patients listed for a liver transplant, with respect to cellular rejection rates. Secondary Objectives: 
 1. To assess the safety of immunotherapy for treatment of HCC in patients listed for a liver transplant, with respect to adverse events during treatment, and graft loss and mortality rates up to 30 days after transplant; 2. To assess the efficacy of immunotherapy for treatment of HCC in patients listed for a liver transplant, with respect to radiologic and pathologic responses, and survival outcomes. Exploratory Objectives: 
 1. To assess the correlation of peripheral blood immune cell profiles with clinical outcomes 2. To assess the correlation of baseline stool sample microbiome profiles with clinical outcomes

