Study Design: ESR-20-21010 is a single-arm, open-label, Phase II, multicenter clinical trial designed to evaluate the safety and efficacy of durvalumab and tremelimumab for the treatment of hepatocellular carcinoma (HCC) patients who have cirrhosis or portal hypertension and are listed for a liver transplant. The key eligibility requirements include HCC, Child-Pugh score of up to 7, and ECOG PS of 0 or 1. Patients will be treated with the immunotherapy combination for up to 4 months. After a minimum 28 day gap following the final durvalumab dose, they will undergo locoregional therapy per institutional standards. Eventually, after a minimum 72-day gap from the end of immunotherapy, they will undergo liver transplant.

The primary endpoint is proportion of patients experiencing post-transplant rejection, graft loss, death, or loss to follow up (within 30 days of transplant). A total of 30 patients are to be enrolled, to allow at least 20 transplants for adequate primary endpoint analysis. An interim analysis after 10 patients will be performed to ensure safety. If there are untoward safety signals, study modification/discontinuation will be taken into consideration by the UCCC DSMB, investigators, the sponsor-investigator and AstraZeneca during the study and at interim analysis.

Number of Centers: 3

Number of Patients: 30

Study Population: HCC patients who have cirrhosis or portal hypertension and are listed for a liver transplant.

Inclusion Criteria:
 
 1. Hepatocellular carcinoma, diagnosed either by biopsy or by combination of cirrhosis and imaging criteria (contrast-enhanced CT or MRI) 2. Tumor confined to liver (no evidence of extrahepatic disease), with no macrovascular invasion 3. Patient evaluated by institutional Liver Transplant team and deemed eligible for transplant 4. Measurable disease by RECIST 1.1 5. No prior therapy for HCC 6. Adult patient (Age ≥ 18) 7. ECOG = 0 or 1 Child-Pugh Score = 5, 6, or 7 8. Creatinine < 1.5 ULN 9. Body weight > 30 kg

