10.4. Interim Safety Analysis

During immunotherapy, grade 3-5 AEs will be monitored and at 10 patients enrolled an interim safety analysis will be performed. We will halt enrollment and assess safety in detail to determine if the study should continue, in discussion with AstraZeneca if:

- Of the first 10 patients, if ≥ 3 patients have to discontinue immunotherapy due to treatment related AEs and/or
- Of the first 10, if ≥ 3 patients experience SAEs related to locoregional therapy after immunotherapy and/or
- Of the first 10, if ≥ 3 patients fail to reach liver transplant due to immunotherapy toxicity and/or
- Of the first 10 patients, if ≥ 3 deaths are encountered, from enrollment to up to 30 days after transplant

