14.2. Sample Size/Accrual Rate

A total of 30 patients are to be enrolled, to allow at least 20 transplants for adequate primary endpoint analysis.

During immunotherapy, grade 3-5 AEs will be monitored. In the pivotal study of durvalumab and tremelimumab (Kelley et al, Abstract 4508 at ASCO 2020), 16% had Tx related (TR) SAEs, and 11% had discontinuation of treatment due to TR AEs. We will use these guardrails for interim safety analyses at 10 patients. We will pause enrollment and assess safety in detail to determine if the study should continue, in discussion with AstraZeneca if:

- Of the first 10 patients, if ≥ 3 patients have to discontinue immunotherapy due to treatment related AEs and/or;
- Of the first 10, if ≥ 3 patients experience SAEs related to locoregional therapy after immunotherapy and/or;
- Of the first 10, if ≥ 3 patients fail to reach liver transplant due to immunotherapy toxicity and/or;
- Of the first 10 patients, if ≥ 3 deaths are encountered, from enrollment to up to 30 days after transplant.

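### The only interim look with numeric pause rules is set at the 10th enrolment with no minimum follow-up, when none of its four rules is complete for all 10 patients

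*Combined protocol and SAP*

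**What the plan says.** Section 10.4 fixes the timing by enrolment: "at 10 patients enrolled an interim safety analysis will be performed". The synopsis says "An interim analysis after 10 patients will be performed to ensure safety", and Section 14.2 says "We will use these guardrails for interim safety analyses at 10 patients"; neither says what the 10 patients must have completed. No section gives a minimum follow-up, a data-maturity condition or a repeat look.

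Sections 10.4 and 14.2 list the same four rules. Each stops enrolment for a detailed safety assessment at 3 or more among the first 10:

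- Rule 1: "patients have to discontinue immunotherapy due to treatment related AEs".
- Rule 2: "patients experience SAEs related to locoregional therapy after immunotherapy".
- Rule 3: "patients fail to reach liver transplant due to immunotherapy toxicity".
- Rule 4: "deaths are encountered, from enrollment to up to 30 days after transplant".

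Section 10.2 allows up to five durvalumab doses at four-week intervals. Locoregional therapy follows at least 28 days after the last dose, and transplant at least 72 days after the end of immunotherapy. Section 14.2 names two reference rates as guardrails for the interim, 16% treatment-related SAEs and 11% discontinuation for treatment-related AEs.

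**The concern.** The rules are written on a denominator of 10, but the trigger is a calendar event at which the 10th patient has contributed no follow-up. Rule 2 cannot count a patient before locoregional therapy. Rule 3 is settled only at transplant or when transplant is ruled out. Rule 4 closes 30 days after transplant. A rule may therefore fail to fire because patients have not been followed long enough, and the result would be recorded as a pass. The protocol's HCC background (Section 6.6) names graft rejection as the major risk and calls the trial a pilot to ensure safety. Yet the one look with numeric pause rules comes before the peri-transplant data on its own patients are complete, and enrolment continues afterwards with no further numeric pause rule.

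**Working it through.** The plan gives no operating characteristics for the interim rules, so there is no stated figure to reproduce. The check has three steps.

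**1. Earliest milestones for a full course**, in days after the first dose (inputs from Section 10.2; the Study Calendar notes also count the 72 days from the final durvalumab dose):

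- Last dose: 4 × 28 = 112
- Locoregional therapy: 112 + 28 = 140
- Transplant: 112 + 72 = 184
- End of the 30-day window: 184 + 30 = 214, or 214 / 30.44 = 7.0 months

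**2. How many of the first 10 could have reached each milestone at the 10th enrolment.** The synopsis gives 30 patients and "Four years to complete accrual". Even accrual is my assumption. The spacing is then 1,461 / 30 = 48.7 days, and patient k has (10 − k) × 48.7 days of follow-up: 438, 390, 341, 292, 244, 195, 146, 97, 49 and 0. The table counts patients at or beyond each milestone.

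| Scenario | Immunotherapy finished | Locoregional therapy possible | Transplant possible | Past day 30 possible |
|---|---|---|---|---|
| 4-year accrual, no waiting time | 7 | 7 | 6 | 5 |
| Same, first dose 28 days after registration (limit in Section 8.4) | 7 | 6 | 5 | 5 |
| 4-year accrual, assumed 3-month wait for a graft | 7 | 7 | 4 | 3 |
| 2-year accrual, no waiting time | 5 | 4 | 2 | 1 |
| 1-year accrual, no waiting time | 0 | 0 | 0 | 0 |

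These counts assume all five doses. A patient who stops after one dose could reach the last three milestones at days 28, 72 and 102. If every patient did so, the first-row counts for locoregional therapy and day 30 would be 9 and 7.

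**3. Chance that a rule fires.** With n informative patients and true event probability p, P(X ≥ 3) = 1 − Σ C(n, x) pˣ(1 − p)ⁿ⁻ˣ over x = 0, 1, 2. At p = 0.30:

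- n = 10: 1 − (0.028 + 0.121 + 0.233) = 0.617
- n = 7: 1 − (0.082 + 0.247 + 0.318) = 0.353
- n = 6: 0.256
- n = 5: 1 − (0.168 + 0.360 + 0.309) = 0.163
- n = 2 or fewer: 0

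For rules 3 and 4 the figures at n below 10 are lower bounds, because toxicity failures and deaths before transplant already count. The same holds for rule 1, since a patient still on immunotherapy may already have stopped for toxicity. Rule 2 has no such early contribution.

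**Time to a complete reading.** The 10th patient enrols at month 9 × 1.6 = 14.4 and can close the last window no earlier than month 14.4 + 7.0 = 21.4. In those 214 days, 214 / 48.7 = 4.4 further patients would enrol, or 214 / 24.35 = 8.8 under 2-year accrual.

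**The case against.** The strongest reply is that the wording of the rules fits a running count, and that the trial is watched throughout. The synopsis lets the DSMB, the investigators and the manufacturer consider modification or discontinuation at any time. Section 17.3 provides regular DSMB review, Section 17.1 gives the lead investigator continuous data access, and Section 15.14 requires SAE reports within 24 hours. The trial is open-label, so events are visible as they occur. All of this stands, and it lowers the risk. It does not close the gap: no section says the rules are cumulative, and none of this oversight carries a numeric pause rule. Section 14.3 does treat graft loss of 7.5% or more as a serious safety signal, but attaches no pause to it.

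A reader might infer that rules 2 to 4 cannot be evaluated at all at the look. The documents do not support that. Rule 4 counts deaths from enrolment, rule 3 can be met by toxicity during immunotherapy, and some patients could have reached locoregional therapy or transplant. Nor is rule 1 the one mature rule: at planned accrual only about 7 of the 10 could have finished a full course.

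A reader might also infer that the look will be passed whatever the true risk. That is wrong: at a 50% event rate with only 5 informative patients, a rule still fires with probability 0.50.

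**Conclusion.** The concern holds in this form: the trigger is an enrolment count without follow-up, none of the four rules is complete for all 10 patients at that point, and rules 2 to 4 are the least mature. They can be breached at the look but not cleared by it. At planned accrual, about 7, 6 and 5 of the first 10 could have reached locoregional therapy, transplant and day 30 after transplant. At a 30% event rate, the chance of firing falls from 61.7% to 35.3% with 7 informative patients and 16.3% with 5, with the lower-bound caveat above.

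The size rests on even accrual, full courses and no waiting-list time. Faster accrual or waiting time makes it worse; early stopping of immunotherapy makes it milder. The finding that the 10th patient's data are immature at the trigger needs none of these assumptions.

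A separate, smaller point is that Section 14.2 presents the 16% treatment-related SAE rate as a guardrail, yet none of the four rules counts immunotherapy-related SAEs. The text and the rules do not match. The documents give no basis for a particular threshold, and none is offered here.

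**What to change.** In Sections 10.4 and 14.2 and the synopsis:

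1. State that each rule is applied cumulatively to the first 10 patients, so that the pause takes effect when the third qualifying event occurs.
2. State that the rules stay open until each of the 10 has passed day 30 after transplant or is known not to be going to transplant.
3. Keep the review at the 10th enrolment, described as an early look, and add a final tabulation when the last of the 10 windows closes.
4. At each look, report to the DSMB how many patients are informative for each rule.
5. Use one definition of the milestone in all three places.
6. Reconcile the cited SAE guardrail with the list of rules.

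The cost is protocol wording and one extra tabulation, with no added patients and no hold on enrolment unless a rule is met. The drawback is that the final reading comes at least 7 months after the 10th patient starts a full course. About 4 more patients may enrol by then, or about 9 under 2-year accrual. The cumulative trigger offsets this, because a third event pauses enrolment whenever it occurs.

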10.5. Duration of Therapy

In the absence of treatment delays due to adverse event(s), treatment may continue for up to 4 months or until one of the following criteria applies:

- Clinical disease progression
- RECIST 1.1 and/or mRECIST defined radiological progression
- Intercurrent illness that prevents further administration of treatment
- Unacceptable adverse event(s)
- Patient decides to withdraw consent for the study treatment
- General or specific changes in the patient's condition render the patient unacceptable for further treatment in the judgment of the investigator
- Patient non-compliance
- Pregnancy
 - All women of child bearing potential should be instructed to contact the investigator immediately if they suspect they might be pregnant (*e.g.*, missed or late menstrual period) at any time during study participation.
- Termination of the study by University of Cincinnati PI
- The drug manufacturer can no longer provide the study agents

The reason(s) for protocol therapy discontinuation, the reason(s) for study removal, and the corresponding dates must be documented in the study EDC (REDCAP) and within study source documentation.

10.6. Duration of Follow-Up

Patients will be followed for up to five years after completion of I/O (whether transplantation occurs or not), or until the subject withdraws consent to all follow-up procedures, is lost to follow-up, or until death, whichever occurs first. Patients removed from study for unacceptable adverse event(s) will be followed until resolution or stabilization of the adverse event. See AE Section 15 for timing of collection and follow-up of AEs and SAEs.

10.6.1. Post-Treatment Safety Visit

The mandatory Post-Treatment Safety Follow-Up Visit should be conducted approximately 28 days (+/- 3 days) after the last dose of durvalumab or before the initiation of a new anti-cancer treatment, whichever comes first. The 30-day post-transplant visit is considered to be a standard of care time-point and is not the point at which the subject enters follow-up status for research purposes, see Survival Follow-up section 10.6.2 below.

10.6.2. Survival Follow-up

Once subjects experience confirmed progression, start a new anti-cancer therapy, or complete the I/O drug treatment regimen then subjects will move into the survival follow-up phase.

Subjects should be contacted by telephone or seen in clinic every 3 months for the first year then every 6 months for 5 years to assess for survival status until death, withdrawal of consent, the subject becomes lost to follow-up or at the end of the study, whichever occurs first. Subjects will be followed up to 5 years.

10.7. Discontinuation from Active Treatment

Discontinuation of study treatment, for any reason, does not impact the patient's participation in the study. A patient who decides to discontinue IP will always be asked about the reason(s) for discontinuation and the presence of any AEs and responses documented in REDCap and within source documentation. The patient should continue attending subsequent study visits, and data collection should continue according to the study protocol. If the patient does not agree to continue in-person study visits, a modified follow-up must be arranged to ensure the collection of endpoints and safety information. This follow-up could be a telephone contact with the patient, a contact with a relative or treating physician, or information from medical records. The approach taken should be recorded in the medical records. A patient that agrees to modified follow-up is not considered to have withdrawn consent or to have withdrawn from the study.

Patients who are permanently discontinued from further receipt of IP, regardless of the reason, will be identified as having permanently discontinued treatment. Patients who are permanently discontinued will enter follow-up (see the study calendar). Patients who permanently discontinue drug for reasons other than objective RECIST and/or mRECIST disease progression should continue to have RECIST scans performed q12 weeks \pm 1 week for the first 48 weeks, and then q12-24 weeks \pm 1 week thereafter until RECIST 1.1 or mRECIST defined radiological PD plus an additional follow-up scan or death (whichever comes first) as defined by the study calendar.

If a patient is discontinued for RECIST 1.1 and/or mRECIST defined progression, then the patient should have 1 additional follow-up scan performed preferably at the next (and no later than the next) scheduled imaging visit, and no less than 4 weeks after the prior assessment of PD.

If a patient is discontinued because they are unable to receive a liver transplant once they have been enrolled onto this study, they will be considered to be "withdrawn" and not a screen-failure. As noted above, discontinuation from study treatment for any reason, including the inability to receive a liver transplant, will not impact a patient's continued participation in this study. The patient should continue attending subsequent study visits, and data collection should continue according to the study protocol as described above within this section.

All patients will be followed for survival until the end of the study. Patients who decline to return to the site for evaluations should be contacted by telephone as indicated in the study calendar as an alternative.

10.8. Lost to Follow-up

Patients who refuse to continue participation in the study, including telephone contact, should be documented as “withdrawal of consent” rather than “lost to follow-up.”

In the absence of a clear withdrawal of consent, study teams should make every attempt to contact subjects during the follow-up phase to determine the patient’s status.

Patients will be considered lost to follow-up only if:

1. 3 phone call attempts on separate days with varying times without establishing contact.
2. If unable to make contact with phone call attempts, a certified letter should be sent to the subject’s last known address.
3. If the certified letter comes back (unable to be delivered), then patient may be considered lost to follow up.
4. If the initial certified letter is not returned as undeliverable in 4 weeks from the date of mailing and patient does not make contact, then a second certified letter should be sent and 4 weeks allowed for any response from the date of mailing.
5. If there is no response to 3 phone attempts or 2 delivered certified mail letters, then the subject may be considered to be lost to follow up.

Investigators should document all attempts to re-establish contact with missing patients throughout the study period. If contact with a missing patient is re-established, the patient should not be considered lost to follow-up and evaluations should resume according to the protocol. In order to support key end points of PFS and OS analyses, the survival status of all patients in the full analysis and the safety analysis sets should be re-checked, this includes those patients who withdrew consent or are classified as “lost to follow up.”

- Lost to Follow up – site personnel should check hospital records, the patients’ current physician, and a publicly available death registry (if available) to obtain a current survival status.

In the event that the patient has actively withdrawn consent to the processing of their personal data, the survival status of the patient can be obtained by site personnel from publicly available death registries (if available) where it is possible to do so under applicable local laws to obtain a current survival status.

10.9. Withdrawal of Consent

Patients are free to withdraw from the study at any time (IP and assessments) without prejudice to further treatment.

Patients who withdraw consent for further participation in the study will not receive any further IP or further study observation, with the exception of follow-up for survival, which will continue until the end of the study unless the patient has expressly withdrawn their consent to survival follow-up. Note that the patient may be offered additional tests or tapering of treatment to withdraw safely.

A patient who withdraws consent will always be asked about the reason(s) for withdrawal and the presence of any AEs. The Investigator will follow up AEs outside of the clinical study.

If a patient withdraws consent, they will be specifically asked if they are withdrawing consent to:

- All further participation in the study including any further follow up (e.g., survival contact telephone calls)
- Withdrawal to the use of any samples

The withdrawal of consent must be documented in REDCap and in source documentation.

10.10. Restrictions During Study Participation

Restrictions during the study are different from exclusion criteria and apply once the patient has been randomized or started on investigational product.

10.10.1. Blood donation

Patients should not donate blood while participating in this study, or for at least 90 days following the last infusion of durvalumab or tremelimumab.

10.11. Pregnancy

The following restrictions apply while the patient is receiving study treatment and for the specified times before and after:

Female patient of child-bearing potential:

- Female patients of childbearing potential who are not totally sexually abstinent (ie, refraining from heterosexual intercourse during the entire period of risk associated with study interventions) and intend to be sexually active with a non--sterilized male partner must use at least 1 **highly** effective method of contraception (Table 3) They should have been stable on their chosen method of birth control for a minimum of 3 months before entering the study and continue to use it throughout the total duration of the drug treatment and the drug washout period (180 days after the last dose of durvalumab + tremelimumab combination therapy). Non-sterilized male partners of a female patient of childbearing potential must use male condom plus spermicide throughout this period. Cessation of birth control after this point should be discussed with a responsible physician. Periodic abstinence, the rhythm method, and the withdrawal method are not acceptable methods of birth control. Female patients should also refrain from breastfeeding throughout this period.

Male patients with a female partner of childbearing potential:

- Non-sterilized male patients who are not abstinent and intend to be sexually active with a female partner of childbearing potential must use a male condom plus spermicide from the time of screening throughout the total duration of the drug treatment and the drug gap period (180 days after the last dose of durvalumab + tremelimumab combination therapy). However, periodic abstinence, the rhythm method, and the withdrawal method are not acceptable methods of contraception. Male patients should refrain from sperm

donation throughout this period. Vasectomised males are considered fertile and should still use a male condom plus spermicide as indicated above during the clinical study.

- Even if the female partner is pregnant, male participants should still use a condom plus spermicide (where approved), as indicated above during the clinical study, if there is a concern about damaging the developing foetus from drug in ejaculate.
- Female partners (of childbearing potential) of male patients must also use a highly effective method of contraception throughout this period (Table 3).

Females of childbearing potential definition:

Are defined as those who are not surgically sterile (ie, bilateral salpingectomy, bilateral oophorectomy, or complete hysterectomy) or post-menopausal. Women will be considered post-menopausal if they have been amenorrheic for 12 months without an alternative medical cause. The following age-specific requirements apply:

- Women <50 years of age would be considered post-menopausal if they have been amenorrheic for 12 months or more following cessation of exogenous hormonal treatments and if they have luteinizing hormone and follicle-stimulating hormone levels in the post-menopausal range for the institution.
- Women ≥50 years of age would be considered post-menopausal if they have been amenorrheic for 12 months or more following cessation of all exogenous hormonal treatments, had radiation-induced menopause with last menses >1 year ago, had chemotherapy-induced menopause with last menses >1 year ago.

Highly effective methods of contraception definitions:

Are defined as one that results in a low failure rate (i.e., less than 1% per year) when used consistently and correctly are described in Table 3. Note that some contraception methods are not considered highly effective (e.g., male or female condom with or without spermicide; female cap, diaphragm, or sponge with or without spermicide; non-copper containing intrauterine device; progestogen-only oral hormonal contraceptive pills where inhibition of ovulation is not the primary mode of action [excluding Cerazette/desogestrel which is considered highly effective]; and triphasic combined oral contraceptive pills).

Table 3. Highly effective methods of contraception (<1% failure rate)

Barrier/Intrauterine methods	Hormonal Methods	Additional Allowed Methods

 • Copper T intrauterine device • Levonorgestrel-releasing intrauterine system (e.g., Mirena®)^a 	
 • Implants: Etonogestrel-releasing implants: e.g. Implanon® or Norplant® • Intravaginal: Ethinylestradiol/etonogestrel-releasing intravaginal devices: e.g. NuvaRing® • Injection: Medroxyprogesterone injection: e.g. Depo-Provera® • Combined Pill: Normal and low dose combined oral contraceptive pill • Patch: Norelgestromin/ethinylestradiol-releasing transdermal system: e.g. Ortho Evra® • Minipill: Progesterone based oral contraceptive pill using desogestrel: Cerazette® is currently the only highly effective progesterone based pill 	
 • Total sexual abstinence (evaluate in relation to the duration of the clinical study and the preferred and usual lifestyle choice of the participant) • Vasectomised sexual partner (with participant assurance that partner received post-vasectomy confirmation of azoospermia) • Tubal occlusion • Intrauterine device (provided coils are copperbanded)

^a This is also considered a hormonal method

